**Protocol Title:** Potential for Cortisol Suppression with the Use of High Volume Nasal Mometasone Irrigations in Varying Dosages

Principal Investigator: [name]

Address: Rush University Medical Center, Department of Otorhinolaryngology – Head and Neck Surgery, [name]

Protocol Version Date: April 20, 2018

Objective:

To determine incidence of cortisol suppression with the use of high volume nasal Mometasone irrigations in varying dosages.

Study Duration: 1 year

Timeframe of study treatment and participation: 12 – 16 weeks

Inclusion Criteria:

- Age 18+
- Diagnosis of Chronic Rhinosinusitis, with or without nasal polyposis
- History of prior endosopic sinus surgery
  - Must include at least ethmoidectomy with maxillary antrostomy

Exclusion Criteria:

- Exposure to systemic corticosteroids within one month of the date of enrollment in to the study.
- Adrenal insufficiency
- Liver disease
- Use of oral estrogens in women
- Morbid obesity (BMI > 38)
- Concurrent pregnancy
- Use of medications which may alter HPA axis(refer to Drugs that affect HPAA)
- Ciliary dysmotility, cystic fibrosis, sarcoidosis, systemic vasculitis, IgG or IgA deficiency, known pituitary or adrenal disease

Intervention:

- 1. Pre study variables to be collected
  - a. Demographic data including MRN, Name, Age, Sex, BMI
  - b. Laboratory data including AM cortisol level and pregnancy testing.
  - c. Imaging data
  - d. Pertinent medical history related to sinus disease

- e. Concomitant medication H/o (Avoid drug interactions refer to the drug interactions section)
- f. Hx of arenal insufficiency and liver disease
- g. Asthma history
- h. Allergy history
- i. ASA intolerance
- j. Smoking history
- k. Lund-Mackay radiographic score
- I. Modified Lund-Mackay endoscopic score
  - i. Only if able to be used preoperative. May be a strictly postoperative scoring system.
- m. Presence/absence of polyps
- 2. Enrolled pts will be randomized on first come first serve into one of the three Mometasone irrigation groups (15 subjects in each dose study group)
  - a. 1mg, 2mg, 4mg BID nasal sinus irrigation dose (see pharmacokinetic calculations in rationale)
- 3. Patients will be followed and treated as standard care. No additional patient visits will be required as part of the research protocol.
- AM cortisol testing will be performed at 12 16 weeks after 12 weeks of continuous topical irrigation use

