  - a. Testing will be performed between 6-10 am
    - i. This is the standard in the literature
    - ii. RUMC lab hours 7am-5:30pm M-F
  - b. If patient requires steroid burst for medical reasons, testing schedule will be delayed 1 month from oral steroid use
- 5. Subjects with abnormal blood cortisol levels after 12 weeks of continuous topical irrigation will have a repeat blood cortisol level tested and if abnormal will be follow up with an Endocrinologist.

Drugs which affect the HPAA:

- Mifepristone
- Cyproheptadine, ketanserin, ritanserin, metergoline
- Bromocriptine, cabergoline
- Reserpine
- Valproic acid
- Octreotide, lanreotide, pasireotide
- Pioglitazone, rosiglitazone
- Metyrapone, Trilostane, mitotane, aminoglutethimide, ketoconazole, fluconazole, etomidate
- Sertraline, citalopram, Trazodone
- Clonidine
- MDMA, cocaine, amphetamine
- Methadone, buprenorphine, naltrexone

- Olanzapine, quetiapine, imipramine, desimipramine, clomipramine, mirtazapine
- Medroxyprogresterone, megestrol, Raloxifene
  Drug Interactions
- Avoid combination with Desmopressin
- Monitor therapy while on
  - A. CYP3A4 Inhibitors (Strong) Interacting Members Atazanavir; Boceprevir; Clarithromycin; Cobicistat; Darunavir; Idelalisib; Indinavir; Itraconazole; Ketoconazole (Systemic); Lopinavir; MiFEPRIStone; Nefazodone; Nelfinavir; Ombitasvir, Paritaprevir, and Ritonavir; Ombitasvir, Paritaprevir, Ritonavir, and Dasabuvir; Posaconazole; Ritonavir; Saquinavir; Telaprevir; Telithromycin; Voriconazole
  - B. Ceritinib.
  - C. Ritodrine

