## Potential for Cortisol Suppression With the Use of High Volume Nasal Mometasone Irrigations in Varying Dosages.

NCT03979209

8/10/2021

Statistical Analysis Plan

An a priori analysis using G\*3.0.10 Power was performed in order to determine adequate sample size. Using a Cohen's D of 1.0, alpha of 0.05 and power of 0.95, sample size was determined to be 13. Pre- and post-treatment morning cortisol serum levels were compared using a match paired, dependent sample Student's *t*test. Significance was established at *P*<0.05. All data acquired during this study were de-identified to protect patient privacy, and identifying information was only available to the principal investigator.

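### With three active doses, no untreated group and only a pre/post test, the plan cannot separate a mometasone effect from other change over 12-16 weeks and gives no comparison between doses

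*SAP*

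**What the plan says.** The objective (Protocol, Objective) is "To determine incidence of cortisol suppression with the use of high volume nasal Mometasone irrigations in varying dosages". Under Intervention, item 2, patients are "randomized on first come first serve into one of the three Mometasone irrigation groups", with "15 subjects in each dose study group". Item 2a gives the groups as "1mg, 2mg, 4mg BID nasal sinus irrigation dose". No placebo, saline-only or untreated group is described.

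Cortisol is measured twice. The pre-study variables (item 1b) include "Laboratory data including AM cortisol level and pregnancy testing". The follow-up item reads "AM cortisol testing will be performed at 12 16 weeks after 12 weeks of continuous topical irrigation use", and beneath it "Testing will be performed between 6-10 am". That clock window appears only under the follow-up test.

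The SAP contains one inferential procedure: "Pre- and post-treatment morning cortisol serum levels were compared using a match paired, dependent sample Student's" t-test, with significance at P<0.05. It gives a sample size of 13 for Cohen's D 1.0, alpha 0.05 and power 0.95. It does not say whether the test is run per dose or on all patients together, or whether it is one- or two-sided. It specifies no comparison between doses, no trend test and no adjusted model.

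**The concern.** Every participant receives mometasone, so the mean change from baseline is the drug effect plus anything else that shifts morning cortisol between the two draws. Candidates that the protocol leaves open are season (draws 12-16 weeks apart within a one-year study), stress at the first draw, and time since surgery (prior sinus surgery is required, with no minimum interval). A paired t-test has no means of separating these from the drug.

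The design does contain something that could help: three concurrent groups over a fourfold dose range. A drift shared by all groups cancels when doses are compared. The SAP does not use this, so the trial as planned yields no estimate of how cortisol changes with dose, although dose is part of the objective. For a safety question the error matters in both directions: a downward drift could pass for suppression, and an upward drift could conceal it.

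**Working it through.** **1. The plan's own figure.** For a paired t-test, noncentrality is d√n with n − 1 df. At d = 1.0, alpha 0.05 and target power 0.95:

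- one-sided exact: smallest n = 13, power 0.960;
- two-sided normal approximation: (1.960 + 1.645)² ≈ 13.0, so n = 13;
- two-sided exact: n = 16 (power 0.962); n = 13 gives 0.911.

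So 13 is reproduced for a single before-after comparison. It does not fit a comparison of two doses: for D = 1.0 and power 0.95, the normal approximation 2 × (1.960 + 1.645)² gives 26 per arm two-sided (27 by exact t).

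**2. Effect of drift on the paired test.** The documents give neither a drift nor an SD, so drift is an assumption, in units of the SD of the within-patient change. With no drug effect, the probability of P<0.05 (two-sided, noncentral t) is:

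| Common drift (SD of change) | One group, n = 15 | At least one of three groups of 15 | All 45 pooled |
|---|---|---|---|
| 0 | 0.050 | 0.143 | 0.050 |
| 0.2 | 0.112 | 0.299 | 0.259 |
| 0.3 | 0.192 | 0.472 | 0.503 |
| 0.5 | 0.438 | 0.822 | 0.907 |

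The third column is 1 − (1 − p)³, for example 1 − (1 − 0.438)³ = 0.822. Its reference value is 1 − 0.95³ = 0.143, not 0.05. The last two columns are alternative readings of a SAP that does not say per dose or pooled.

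If the test is one-sided and drift runs in the tested direction, the ranges for drift of 0.2-0.5 SD are 0.182-0.578 for n = 15 and 0.373-0.951 for 45 pooled.

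**3. The same table read for masking.** The test sees only the net shift. A true fall of 0.5 SD with an upward drift of 0.3 SD leaves 0.5 − 0.3 = 0.2 SD. The chance of detection drops from 0.438 to 0.112 in a group of 15, and from 0.907 to 0.259 pooled. At the planned effect of 1.0 SD, an upward drift of 0.5 SD takes a group of 15 from 0.949 to 0.438.

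**4. What a dose comparison offers.** In a model with dose as a covariate, a drift common to all groups enters only the intercept, so the test of the slope keeps its level. A simulation of 20,000 trials with a drift of 0.5 SD, no drug effect and a linear dose-trend test on change scores gave 5.0% rejection, against 90.5% for the pooled paired test.

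Its power is limited. Code log2(dose) as −1, 0, 1 with 15 per group: Sxx = 15 × (1 + 0 + 1) = 30, and noncentrality is slope × √30 with residual SD 1. The 4 mg minus 1 mg difference is two doublings, or twice the slope.

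- Difference 1.0 SD (slope 0.5): noncentrality 2.74, power 0.76.
- Difference 0.5 SD (slope 0.25): noncentrality 1.37, power 0.27.

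The standard error of the difference is 2/√30 = 0.365 SD. With 45 − 3 = 42 df (t = 2.018), the 95% interval is about ±2.018 × 0.365 = ±0.74 SD.

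**The case against.** Several points on the other side stand in part.

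- **Safeguards.** The protocol sets a 6-10 am window for the follow-up draw, delays testing one month after a steroid burst, repeats abnormal results, and excludes recent systemic steroids and HPA-altering drugs. These limit several sources of change. They do not remove drift: the window is four hours wide and is not written for the baseline draw.
- **No rule of attribution.** A reader might infer that the plan treats any pre/post change as a drug effect. The SAP does not say so; it names a comparison and a significance level. What holds is that the analysis cannot tell the two apart.
- **Assumed drift.** Nothing in the documents shows that drift of 0.2-0.5 SD occurs. Seasonal shifts may partly cancel if enrolment is spread over the year. The figures illustrate sensitivity and are not an estimate of this trial's error rate.
- **Regression to the mean.** This is a tempting addition, but eligibility sets no cortisol threshold, so there is little selection on baseline to drive it. It is not relied on here.
- **Limits of the dose comparison.** It misses an effect equal at all doses and is weak for moderate gradients. It would therefore be wrong to make a dose gradient a condition for reporting a fall: in a safety study, that could set aside a real fall common to all doses.
- **Allocation.** First-come-first-served randomisation leaves the method unclear. If groups were filled in sequence, calendar drift would be confounded with dose and the protection in step 4 would not apply.

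**Conclusion.** The point holds in this form: the plan has no untreated group, its only test is pre/post, and it specifies no comparison between doses. A pre/post change cannot by itself be attributed to mometasone, nor can the lack of one exclude suppression. Under an assumed common drift of 0.2-0.5 SD of change and a two-sided test, rejection with no drug effect is 11-44% in a group of 15 and 26-91% pooled (nominal 5%), and 30-82% for at least one of three groups (14% without drift).

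The documents do not support two stronger readings: that the sponsor has committed to a causal interpretation, or that the trial is known to have an inflated false-positive rate. Nor can the dose model replace a control group. It isolates only the dose-related part of an effect, only if allocation was random, and with useful power only for differences near 1 SD between 4 mg and 1 mg.

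**What to change.** In the SAP:

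1. Keep the paired comparison, stated as within each dose group.
2. Add an ANCOVA of 12-16 week AM cortisol on log2(dose), adjusted for baseline AM cortisol. Report the slope per dose doubling and the 4 mg minus 1 mg difference, each with a 95% confidence interval, and treat the intervals as the main result.
3. State that the pre/post change cannot by itself be attributed to mometasone, and that absence of a detected dose gradient is not evidence of no suppression.
4. Describe how allocation was actually done. If it was sequential, say that the dose comparison is not protected against calendar drift.
5. The SAP is dated 8/10/2021 and written in the past tense. If the model is added after the data were seen, label it post hoc.

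The cost is SAP wording and one model on data already planned for collection, with no new patients or visits. The price is a more modest conclusion: the contrast is imprecise at 15 per group and cannot detect an effect equal at all doses.
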